Date: April 9, 2019

Title: Importance of Sock Type in the Development of Foot Lesions on Low-difficulty, Short Hikes.

Description of document: Materials and Methods (Study Protocol: description of the clinical study, including objective and design. Statistical Analysis Plan (description of the statistical considerations for analyzing the data collected in the study.) results of the study (Results obtained in the study) and Supplementary data (protocol of measures and other tables).

Materials and Methods

1. Permission and participants

All participants signed an informed consent form, and permission for the study was obtained from the Bioethics Committee (reference 126/2016). The admission criteria were: be of legal age, have no current health problems that would hinder or prevent participation in the hike, and carry a backpack weighing less than 3 kg. Participants were asked to use specific hiking footwear (light, flexible, soft-soled, with good grip and breathable material) (low top hiking shoes), based on earlier studies [38-40]. They were also asked to do the entire hike following the instructions of an experienced guide and to not remove their footwear or socks before examination by a podiatrist.

2. Sock type and interventions performed

Socks were of two types: technical socks, designed for high performance sports use (Lurbel brand, models Tierra and Set), and non-technical socks for everyday use. The socks had different composition: Tierra (50% regeneractiv, 25% cool-teak, 17% polyamide ions, 8% lycra); Set (75% cotton, 17% polyamide, 8% lycra) and cotton (98% cotton, 2% elastane). The technical socks had reinforced weave in the toe, metatarsal and heel areas.

Participants were examined by trained podiatrists on three occasions to measure the study variables: at the start of the walk (km 0), at the end of the asphalt section (half way; km 14.5) and at the end (km 29.6). The protocol of measures was followed (supplementary data).

3. Study design, route description and participants

Weight (kg)

A clinical trial randomized, double blinded was designed to analyze the influence of different types of socks (technical and non-technical) on the appearance of foot injuries after a low-difficulty, short-term sport activity. The study follow the CONSORT criteria.

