To carry out the study, the hiker was previously registered. The researchers contacted the participants to explain the study. In addition, data on age, sex, foot number and associated diseases that prevented the completion of the route were obtained. One hour before starting the route, researchers who did not intervene in the exploration process, made registration and delivery to each hiker of two technical socks (1 Set and 1 Tierra) appropriate to the size of the foot and randomly for the right foot (RF) and left foot (LF). Likewise, it proceeded for non-technical socks (cotton), but in this case both feet wore the same type of sock. All the participants before the initial exploration had their socks put on for half an hour. The hike was low-difficulty, over a short distance [37]. The first 14.5 km were on asphalt and the last 15.1 km on dirt. The height range was 189 m and the pace was moderate, at 5 km/hour. The sample comprised 109 participants (53 men and 56 women). Two women had to give up the hike for personal reasons. Both wore technical socks.

The Table 1 explain the anthropometric characteristics of the participants and the distribution of the socks, differentiating by sex and feet.

Anthropometric variable	Total	Male	Female	
Gender		48.6%	51.4%	
Age (years)	44± 25	49± 21	36 ± 24	
Height (meters)	1.7± 0.1	1.7± 0.1	1.6± 0.1	

81.0±13.5

61.4±7.8

68.8±19.4

Table 1. Anthropometric variables, total sock distribution and sock distribution by gender.

BM	II	24.9± 3.6	26.6± 3.7	23.5± 9.1
Sock type di	istribution	Total %	Male %	Female %
LF sock	Tierra	40.4 (n=44)	35.8 (n=19)	44.6 (n=25)
	Set	29.4 (n=32)	35.8 (n=19)	23.3 (n=13)
	Cotton	30.2 (n=33)	28.4 (n=15)	32.1 (n=18)
RF sock	Tierra	29.4 (n=32)	35.8 (n=19)	23.3 (n=13)
	Set	40.4 (n=44)	35.8 (n=19)	44.6 (n=25)
	Cotton	30.2 (n=33)	28.4 (n=15)	32.1 (n=18)

Km=Kilometres, n=sample size, %=Percentage, ±=Standard deviation, kg=Kilogrammes, BMI=Body mass index, LF=Left foot, RF=Right foot.

4. Study variables

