The qualitative variables analysed were: gender, body mass index (BMI) by rank, sock type, dermal lesions (all lesions developed during the hike, both keratopathies with keratinisation disorder and dermatopathies without keratinisation disorder), muscle lesions (all lesions developed during the hike) and nail lesions (all nail lesions developed during the hike, both traumatic and non-traumatic onychopathies). The height and weight data obtained were used to calculate BMI by rank, interpreted according to the World Health Organization classification [41] (Table 2).

Table 2. Qualitative variables and categories. BMI= Body mass index.

Qualitative variable	Category	
Gender	Male Female	
BMI	Underweight (<18.5) Normal weight (18.5-24.99) Overweight (25.0-29.9) Obese ((>30)
Sock type	Technical (Tierra) Technical (Set) Non-technical (Cotton)	
Skin lesion	Blister Injury (Erosion & chafing) Reddened skin Urticaria Crevice H	Ieloma
Muscle lesion	Pain due inadequate warm Inflammation Muscle discomfort Sprain	
Nail lesion	Onychocryptosis Subungueal hematoma	

The quantitative variables analysed were: age, body mass index (BMI), temperature of each foot measured in two aspects (plantar and dorsal), and perimeter of each foot, measured in four areas (dorsal aspect of toes, instep, heel, tibia).

5. Measuring instruments

The height range and the pace hikers was controlled with a Garmin ETREX 20X GPS (Global Positioning System). Perimeter was measured with a flexible, non-elastic tape measure (Lawton 18-0160, precision 1 mm). Weight was measured using scales (Tanita UM-076, precision 0.1kg) and height was measured using the weight rod of different scales (SECA 704, precision 1 mm).

Temperatures were taken with an infrared thermometer (FTN Medisana, precision 0.18° C), calculating the mean of the three measurements. An intra rate of the measure was done to detect the error of the measure of the temperature, obtaining an error of 0.1452.

6. Statistical tests

The data were analysed using IBM SPSS Statistics for Windows, Version 22.0 (IBM, Armonk, New York). The statistical treatment consisted of data study and cleansing, descriptive variable analysis, normality test (Shapiro-Wilks test). The studies of normality were no significant (p-values between 0.000 y 0.044).

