Quantitative variables depending on whether the samples were paired or independent, Friedman's test for related samples and Kruskal-Wallis was performed for independent samples, both with Bonferroni correction for multiple testing was applied. For the qualitative variables the

chi-square or Fisher's exact test with a significance level of α = 0.05 was carried out. The variables analysed by logistic regression were quantified using the ODDS Ratio (OR). The effect size for the different variables was also calculated. First, for Kruskall-Wallis tests, the variation was between 0.443 y 0.888, and for Friedman tests, the variation was between 0.336 y 0.623. Therefore, in both cases the effect size could be considered median and high.

All p-values = 0.000 are less than 1 per 1000.

Results

After completing the first part of the hike, the most frequent dermal lesions among participants were blisters and erosions.

Table 3. Prevalence of skin, muscle and nail lesions during the 0-14.5 km of the hike by sex.

(0.14 = 1)				Fen	nale					Ma	ıle		
(0-14.5 km)		Tier	ra %	Se	et %	Cott	on %	Tier	ra %	Set	%	Cott	on %
Skin lesion	%Tt.	RF	LF	RF	LF	RF	LF	RF	LF	RF	LF	RF	LF
Blister	12.8	0.0	4.0	8.0	7.7	22.2	27.8	0.0	5.3	5.3	0.0	6.7	13.3
Erosion	2.8	0.0	0.0	0.0	0.0	11.1	5.6	0.0	0.0	0.0	0.0	6.7	0.0
(0.44.5.1)				Fer	male					Ma	ıle		
(0-14.5 km)		Tier	ra %	Se	et %	Cott	on %	Tier	ra %	Set	%	Cott	on %
Muscle lesion	%Tt.	RF	LF	RF	LF	RF	LF	RF	LF	RF	LF	RF	LF
Pain due inadequate warm	21.1	23.1	27.8	8.0	7.7	27.8	27.8	10.5	15.8	10.5	0.0	13.3	13.3
Inflammation	2.8	0.0	4.2	4.0	0.0	0.0	0.0	0.0	10.5	10.5	0.0	0.0	0.0
Muscle discomfort	1.8	0.0	0.0	0.0	0.00	0.0	0.0	5.3	5.3	0.0	0.0	0.0	0.0

Km=Kilometres, %=Percentage, Tt=Total, RF=Right foot, LF=Left foot.

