None of the other dermal lesions included in the evaluation (reddened skin, urticaria, crevice and heloma) were detected. Significant differences were found between the percentage of dermal lesions in hikers wearing technical socks (6.6%) and non-technical socks (36.4%) (p-value=0.000). The women had a higher percentage of dermal lesions (23.2%) than the men (7.5%) (p-value=0.034), regardless of sock type. Moreover, the percentage of women with dermal lesions was significantly higher among wearers of non-technical socks (50%) than in wearers of technical socks (10.5% had lesion) (p-value=0.002). Particularly the women presented more blisters in both RF and LF when they wore cotton sock compared to the Tierra and Set socks (RF p-value = 0.050, LF p-value = 0.042). In the case of men, there was no difference in any of the skin lesions at 14.5 km on any foot compared to the sock used (Table 3). The most frequent muscle lesions at the end of the first part of the hike were pain due inadequate warm (21.1%), inflammation (2.8%) and muscle discomfort (1.8%). No sprains or nail disorders were detected at the end of the first part of the hike. No difference between any of muscle lesions analyzed and technical and non-technical socks were found. By sex, no differences were found regarding technical and non-technical socks or concerning the model used sock on each foot (Table 3).

Table 4. Prevalence of skin, muscle and nail lesions during the 14.5-29.6 km of the hike by sex.

(14.5-29.6 km)				Fema	ale					N	I ale		
(14.5-29.6 KM)		Tie	rra %	Set	%	Cott	on %	Tier	ra %	Se	et %	Cott	on %
Skin lesion	%Tt.	RF	LF	RF	LF	RF	LF	RF	LF	RF	LF	RF	LF
Blister	19.6	7.7	12.0	20.0	7.7	25.0	12.5	5.3	0.0	5.3	21.1	6.7	0.0
Erosion	7.5	0.0	4.0	8.0	0.0	12.5	18.8	0.0	0.0	0.0	0.0	20.0	13.3
Reddened skin	3.7	0.0	0.0	0.0	0.0	18.8	18.8	0.0	0.0	0.0	0.0	6.7	6.7
Urticaria	0.9	0.0	0.0	0.0	0.0	6.3	6.3	0.0	0.0	0.0	0.0	0.0	0.0
Crevice	0.9	0.0	0.0	0.0	0.0	0.0	0.0	0.0	0.0	0.0	0.0	6.7	0.0
Heloma	0.9	0.0	0.0	0.0	0.0	0.0	0.0	0.0	0.0	0.0	0.0	6.7	6.7
(14.5-29.6 km)			Female			Male							

		Tier	ra %	Set	t %	Cott	on %	Tier	a %	Se	et %	Cott	on %
Muscle lesion	%Tt.	RF	LF	RF	LF	RF	LF	RF	LF	RF	LF	RF	LF
Pain due inadequate warm	11.2	15.4	4.0	4.0	7.7	0.0	12.5	10.5	0.0	5.3	10.5	0.0	0.0
Inflammation	0.9	0.0	4.0	4.0	0.0	0.0	0.0	0.0	0.0	0.0	0.0	0.0	0.0
Muscle discomfort	0.9	0.0	0.0	0.0	0.0	0.0	0.0	0.0	0.0	5.3	0.0	0.0	0.0
Sprain	0.9	0.0	0.0	4.0	0.0	0.0	0.0	0.0	0.0	0.0	0.0	0.0	0.0
(14.5-29.6 km)				Fem	ale					N	Iale		

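### The objective covers the whole hike, but skin and muscle lesions are tested only within each half, so no whole-hike sock effect is estimated for them; the tables give only limits for skin lesions.

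*Combined protocol and SAP*

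**What the plan says.** The design paragraph (Combined protocol and SAP, Materials and Methods, section 3) gives the aim as the influence of sock type "on the appearance of foot injuries after a low-difficulty, short-term sport activity". Section 4 defines the skin outcome as "dermal lesions (all lesions developed during the hike", and defines muscle and nail lesions in the same way. Socks were issued once, before the start. Section 6 says that, for qualitative variables, "chi-square or Fisher's exact test with a significance level of α = 0.05 was carried out"; it names no main lesion comparison and no time window.

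The Results then work by segment. Table 3 is titled "Prevalence of skin, muscle and nail lesions during the 0-14.5 km of the hike by sex" and Table 4 "Prevalence of skin, muscle and nail lesions during the 14.5-29.6 km of the hike by sex". The technical versus non-technical tests in the text follow the same split: for the first half, hikers "wearing technical socks (6.6%) and non-technical socks (36.4%) (p-value=0.000"); for the second half, 21.1% against 54.8%, p = 0.001. Table 7, on the logistic regression, is captioned as covering the entire hike but is also divided by distance.

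On numbers and withdrawals, section 3 states: "The sample comprised 109 participants (53 men and 56 women"), and "Two women had to give up the hike for personal reasons. Both wore technical socks".

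**The concern.** One allocation, one hike and an outcome defined over that hike call for one comparison: did the hiker develop a new lesion by the end, yes or no, by sock type? That comparison is absent for skin and muscle lesions. Two segment results stand in its place, further divided by sex, foot and lesion type.

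The second-half result cannot serve as the end-of-hike total, because Table 4 is not cumulative. Without a hiker-level cross-tabulation of first-half by second-half lesions, the reader cannot tell how far the two injured groups overlap. What is at stake is the size of the effect, and whether the finding holds within each sex.

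**Working it through.** **Inputs.** Table 1 gives 33 cotton hikers (18 women, 15 men). Technical wearers are therefore 109 − 33 = 76 (38 women, 38 men). Tests below are Fisher's exact test, taken as two-sided because the plan does not say, and unadjusted.

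**Reproducing the stated figures.**
- First half, all: 5/76 = 6.6% vs 12/33 = 36.4%, p = 0.0002 (stated 0.000).
- First half, women: 4/38 = 10.5% vs 9/18 = 50%, p = 0.0021 (stated 0.002). By subtraction, men are 1/38 and 3/15. As a check, women 13/56 = 23.2% and men 4/53 = 7.5%, as stated.
- Second half, all: 16/76 = 21.1% vs 17/31 = 54.8%, p = 0.0011 (stated 0.001).
- Second half, women: 10/38 = 26.3% vs 11/16 = 68.8%, p = 0.0057 (stated 0.006).
- Second half, men: 6/38 = 15.8% vs 6/15 = 40%, p = 0.076 (stated not significant).

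**Which arm lost two hikers.** The second-half figures need 31 cotton hikers, 16 of them women. With 33 cotton hikers the nearest values are 17/33 = 51.5% and 18/33 = 54.5%; with 18 cotton women they are 12/18 = 66.7% and 13/18 = 72.2%. Removing two technical women would give 16/74 = 21.6% and 10/36 = 27.8%, not 21.1% and 26.3%. Table 4 agrees: the cotton women's cells (6.3, 12.5, 18.8) are sixteenths, while the technical women's cells keep denominators of 25 and 13. This contradicts section 3.

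**Table 4 is not cumulative.** Left-foot blisters in cotton women go from 27.8% (5/18) to 12.5% (2/16). Even if both removed women had blisters, a cumulative count could fall only from 5 to 3. In cotton men the figure goes from 13.3% (2/15) to 0.

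**Limits for a skin lesion in either half.** Within each sex and arm, with a and b injured in the two halves and n hikers, the number injured at least once lies between max(a, b) and min(n, a + b).

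| Group | n | a | b | Limits |
|---|---|---|---|---|
| Technical women | 38 | 4 | 10 | 10-14 |
| Technical men | 38 | 1 | 6 | 6-7 |
| Cotton women | 18 | 9 | 11 | 11-18 |
| Cotton men | 15 | 3 | 6 | 6-9 |

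- Technical: 16-21 of 76 (21.1% to 27.6%).
- Cotton: 17-27 of 33 (51.5% to 81.8%).
- Smallest difference: 17/33 − 21/76 = 23.9 points (odds ratio 2.8, p = 0.028).
- Largest difference: 27/33 − 16/76 = 60.8 points (odds ratio 16.9, p < 0.001).
- The largest p over all admissible pairs of counts is 0.028.

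**By sex, at the least favourable limit.** Women: 14/38 vs 11/18, p = 0.149. Men: 7/38 vs 6/15, p = 0.155.

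**The two who stopped, taken as cotton women.** The limits above use only their first-half status. If both are counted as uninjured, cotton women are 11-16 and the cotton total is 17-25 of 33. If both are counted as injured, cotton women are 13-18 and the total is 19-27 of 33.

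**The case against.** The split follows the design. Examinations were set at three points, the surface changes from asphalt to dirt at 14.5 km, and the measurement form records lesions by segment. The segment analyses are legitimate and worth keeping. This does not supply the missing comparison, because the objective and the lesion definition are not segment-specific.

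Some stronger readings are tempting but not supported:
- A reader might infer that the overall skin conclusion is open. It is not: every admissible table favours technical socks, by at least 23.9 points.
- A reader who pools the sexes would add 12 + 17 = 29 of 33 cotton hikers and reach a difference of about 67 points. That is impossible: 9 + 11 = 20 exceeds the 18 cotton women.
- A reader might extend the point to all lesions. Nail lesions, sprain, reddened skin, urticaria, crevice and heloma were not seen in the first half, so their second-half comparison is in effect already whole-hike, apart from the two who stopped.
- A reader might fault the second-half test for keeping hikers already injured at 14.5 km. That is no error: dropping them would condition on a post-allocation outcome that differs by sock (6.6% vs 36.4%).

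It is also fair to say that the contradiction over the two who stopped is a reporting problem in its own right. It belongs here because it sets the denominator of any whole-hike analysis.

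**Conclusion.** The point holds for skin and muscle lesions. No whole-hike sock effect is estimated for either. For skin lesions the size is known only to lie between about 24 and 61 points; the overall direction is secure. Within each sex the limits do not settle significance. For muscle lesions no per-hiker technical versus cotton counts are published, so not even limits follow.

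The limits rest on counts back-calculated from rounded percentages, which reproduce the stated p-values, and on the two missing hikers being cotton women. If they did wear technical socks, the second-half denominators are wrong and the limits must be recalculated. The first-half percentages use all 56 women, which suggests but does not establish that both were examined at 14.5 km; the documents do not say when they stopped.

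This is a worthwhile change that supplies the missing estimate; it does not overturn the overall skin result.

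**What to change.** - Make the main lesion analysis at least one new dermal lesion at either checkpoint (0-29.6 km), one record per hiker, technical versus cotton, on all 109. Report the risk difference and odds ratio with 95% confidence intervals.
- Do the same for muscle lesions.
- For the two who stopped, use the recorded 14.5 km status if they were examined there. Show the result also with both counted as injured and with both counted as uninjured.
- Reconcile their sock type across section 3 and the second-half results, and correct whichever is wrong: the text or the denominators.
- Keep the half-by-half tables as secondary, and label the combined analysis as added after the segment results were known.

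The cost is one derived variable for each of the two lesion classes and a short table, from data already on the measurement form. The downside is that the segment tests lose prominence.

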(14.5-29.0 KIII)		Tier	ra %	Set	t %	Cott	on %	Tierr	a %	Se	et %	Cott	on %
Nail lesion	%Tt.	RF	LF	RF	LF	RF	LF	RF	LF	RF	LF	RF	LF
Onychocryptosis	0.9	7.7	0.0	0.0	0.0	0.0	0.0	0.0	0.0	0.0	0.0	0.0	0.0
Subungual hematoma	1.9	0.0	0.0	0.0	0.0	6.3	6.3	0.0	0.0	0.0	0.0	6.7	6.7

Km=Kilometres, %=Percentage, Tt=Total, RF=Right foot, LF=Left foot.

In the second part of the hike, a greater variety of dermal lesions was detected. The most prevalent were blisters, erosions and reddened skin. Again, no urticaria, reddened skin, crevices, or helomas were detected with either technical sock. Differences were found between the percentage of dermal lesions among hikers wearing technical socks (21.1%) or non-technical socks (54.8%) (p-value=0.001). By gender, the percentage of women and men with dermal lesions was higher among wears of non-technical socks (women 68.8% and men 40%) than among wearers of technical socks (women 26.3% and men 15.8%) but the differences only were significant in women (p-value=0.006). Considering the sock used in each foot, in the case of women, presented more reddened skin in both RF and LF if they used cotton sock compared to the Tierra and Set (RF and LF p-values=0.023). In the case of men, they presented more blisters in the LF if they used Set sock than cotton or Tierra (p-value=0.021) and more erosion in the RF if they used cotton sock in comparison with the Tierra or Set (p-value=0.018) (Table 4). A greater variety of total muscle lesions was also detected in the second part of the hike: pain due to inadequate warm, inflammation, muscle discomfort and sprain. No differences were found between any of the muscular injuries analysed and the technical and non-technical socks neither by sex (Table 4).

Nail lesions like onychocryptosis (0.9%) and subungual hematomas (1.9%) were infrequently and developed only in the second part of the hike. No difference between any of the nail lesions analyzed and technical and non-technical socks were found. By sex, no differences were found (Table 4).

The temperature comparisons between technical and non-technical socks, regardless of distance, foot, measurement area and sex, showed significant differences. The Friedman test was performed (p value <0.005) for the comparisons between paired samples and the Kruskal-Wallis test was performed (p value <0.009) for independent samples. (Supplementary data, tables A, B).

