By gender, no significant differences were detected between technical socks models nor in women (p-values> 0.287) nor in men (p-values> 0.249). However, significant differences were detected between each model of technical socks and the non-technical sock for all distances and areas of the feet measured (Tierra-Cotton p-values<0.013 in women and p-value<0.036 in men) and (Set-Cotton p-values<0.036 in women and p-value<0.014 in men). Regarding the distance in both men and women, differences were observed from the beginning to the end and from the beginning to the middle route with all the models. In addition, in the case of men the tendency is observed in the plant of both feet to increase the temperature from the middle to the end of the hike (LF p-value=0.056, RF p-value=0.091) although it cannot be considered statistical significance (tables 5 and 6).

Table 6. Men's foot temperature by sock type.

					MAL	.E			
Distanc		Sock		P	-value sock]	P-value dista	nce
e (km)	T	S	С	T-S	T-C	S-C	Т	S	С
]	Dorsal temp	(°C) RF			
0	34.	35.1	22.0	1.000	0.000*	0.000*	(1)=0.005	(1)=0.017	(1)=0.003*
	9						*	*	
14.5	35.	36.1	32.9	1.000	0.030*	0.014*	(2)=0.000	(2)=0.000	(2)=0.000*
	9						*	*	
29.6	36.	36.4	30.0	1.000	0.000*	0.000*	(3)=0.470	(3)=0.223	(3)=0.896
	3								
]	Dorsal tem	p (ºC) LF			
0	35.	35.3	21.4	1.000	0.000*	0.000*	(1)=0.008	(1)=0.240	(1)=0.003*
	2						*		
14.5	36.	36.0	32.5	0.931	0.036*	0.002*	(2)=0.000	(2)=0.003	(2)=0.000*
	3						*	*	
29.6	36.	36.4	30.8	1.000	0.000*	0.000*	(3)=0.128	(3)=0.401	(3)=0.558
	5								
				I	Plantar tem	p (ºC) RF			
0	34.	35.1	22.0	1.000	0.000*	0.000*	(1)=0.011	(1)=0.017	(1)=0.004*
	9						*	*	
14.5	35.	36.4	30.3	0.249	0.007*	0.000*	(2)=0.000	(2)=0.000	(2)=0.001*
	8						*	*	
29.6	36.	36.4	29.0	1.000	0.000*	0.000*	(3)=0.091	(3)=0.223	(3)=1.000
	2								
				I	Plantar tem	p (ºC) LF			
0	35.	34.9	21.8	1.000	0.000*	0.000*	(1)=0.006	(1)=0.001	(1)=0.042*
	0						*	*	

14.5	36. 1	35.7	31.2	0.287	0.000*	0.000*	(2)=0.000	(2)=0.000	(2)=0.000*
29.6	36.	36.2	29.3	1.000	0.000*	0.000*	(3)=0.056	(3)=0.401	(3)=0.558

Km=Kilometres, T=Tierra, S=Set, C=Cotton, Dif.=Difference Temp=Temperature, (${}^{\circ}$ C)=Degrees centigrade, RF=Right foot, LF=Left foot, (*)=Significant difference, (1)= Distance between 0-14.5 Km, (2)= Distance between 0-29.6 Km, (3)= Distance between 14.5-29.6 Km.

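### Tierra and Set were randomised to opposite feet of the same hiker (76 pairs), but no within-hiker comparison of the two models is specified or reported

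*Combined protocol and SAP*

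**What the plan says.** Section 3 (Study design, route description and participants) issues each hiker in the technical arm with "two technical socks (1 Set and 1 Tierra) appropriate to the size of the foot and randomly for the right foot (RF" and left foot. For cotton it adds "but in this case both feet wore the same type of sock", so only the technical arm carries a within-hiker contrast.

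Table 1 mirrors this: Tierra on the left foot in 44 hikers and Set on the right in 44; Set on the left in 32 and Tierra on the right in 32.

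For lesions, section 6 (Statistical tests) names the "chi-square or Fisher's exact test with a significance level" of 0.05. For quantitative variables it names Friedman for related samples and Kruskal-Wallis for independent samples, with Bonferroni correction. In the tables, the related-sample p-values are those for distance.

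The Results report two things on Tierra versus Set. For men's second-half lesions, "they presented more blisters in the LF if they used Set sock than cotton or Tierra (p-value=0.021". For temperature, "no significant differences were detected between technical socks models nor in women (p-values> 0.287) nor in men (p-values> 0.249".

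**The concern.** When two treatments are randomised to the two feet of one person, the natural comparison is between those feet. Hiker, route, pace and body weight are then held constant. The report instead takes one foot at a time and compares hikers with Tierra on that foot with other hikers who had Set on it. Each such test is valid on its own, since it uses one foot per hiker, but it discards half the feet and all of the pairing.

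Readers are left with a blister finding confined to one sex and one side, and with temperature tests that are non-significant after Bonferroni adjustment (many at 1.000) and carry no estimate or interval. Neither tells them how large a Tierra-Set difference the data support or exclude.

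**Working it through.** **Inputs.** Group sizes come from Table 1, lesion percentages by foot from Tables 3 and 4, and hiker-level percentages from the Results text. Counts are percentage times group size.

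**Pairs.** 44 + 32 = 76: men 19 + 19 = 38, women 25 + 13 = 38.

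**Reproducing p=0.021.** Men, left foot, second half, blisters: Tierra 0/19, Set 4/19 (21.1%), cotton 0/15.
- Expected lesion counts are 19×4/53 = 1.43, 1.43 and 15×4/53 = 1.13. Pearson chi-square is 7.74 on 2 df, p=0.0208, which matches the report. The test is therefore an uncorrected three-group comparison of different men.
- The exact three-group test gives p=0.031.
- Set versus Tierra alone on that foot gives Fisher p=0.105.
- On the men's right foot Table 4 shows 5.3% for both models (1/19 each).

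**Men, second half, paired.** Tierra feet 1 + 0 = 1; Set feet 1 + 4 = 5. The text gives 15.8% of technical men with a skin lesion, which is 6/38. Six affected hikers and six affected feet mean that no man had both feet affected. Discordant pairs are 5 Set to 1 Tierra. Exact McNemar: 2×(1+6)/2⁶ = 0.219.

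**All pairs, second half, blisters.**
- Women: Tierra 1 + 3 = 4, Set 5 + 1 = 6. With the men, Set 11 feet and Tierra 5.
- Blistered hikers in total: 19.6% = 21/107. Subtract 6 technical men, 1 cotton man and 4 to 6 cotton women (right 4/16, left 2/16, overlap unknown). That leaves 8 to 10 technical women sharing 10 blistered feet, so 0 to 2 had both feet blistered.

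| Both feet blistered | Set : Tierra discordant | Exact McNemar p | Paired odds ratio (95% CI) |
|---|---|---|---|
| 0 | 11 : 5 | 2×6885/65536 = 0.210 | 2.2 (0.70 to 8.1) |
| 1 | 10 : 4 | 2×1471/16384 = 0.180 | 2.5 (0.72 to 10.9) |
| 2 | 9 : 3 | 2×299/4096 = 0.146 | 3.0 (0.75 to 17.2) |

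The intervals are exact binomial limits for the share of discordant pairs, converted to odds.

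**First half, skin lesions.** Set feet 2 + 1 + 1 + 0 = 4; Tierra feet 0 + 1 + 0 + 1 = 2. Affected technical hikers: 6.6% = 5/76, of whom 10.5% = 4/38 are women, so one man had both feet affected. Discordant 3:1, p = 2×(1+4)/2⁴ = 0.625.

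**Is pairing what changes the answer?** No. Unpaired Fisher pooled over both feet gives 0.200 in men (5/38 v 1/38) and 0.185 overall (11/76 v 5/76).

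**Temperature efficiency.** Let rho be the correlation between a hiker's two feet; the documents give no value.
- Using both feet instead of one: (1/32 + 1/44)/(2/76) = 2.05 times less variance.
- Pairing on top of that: (2/76)/(2(1−rho)/76) = 1/(1−rho). This is 1 at rho = 0, 2 at an assumed 0.5 and 5 at an assumed 0.8.

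**Number of second-half pairs.** Section 3 says of the dropouts: "Two women had to give up the hike for personal reasons. Both wore technical socks". That leaves 74 pairs. The Results give "the percentage of dermal lesions among hikers wearing technical socks (21.1%) or non-technical socks (54.8" per cent. 21.1% is 16/76 (16/74 = 21.6%) and 54.8% is 17/31 (18/33 = 54.5%). The percentages therefore place both dropouts in cotton, against the text.

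**The case against.** The stated objective is technical versus non-technical socks, so Tierra versus Set is secondary. For lesions, pairing hardly moves the p-value. The fragility of 0.021 comes from splitting by foot and sex, including cotton and testing sparse cells. All of this stands, and it limits the weight of the point. It does not remove it: sock type has three categories in Table 2, and the report itself draws conclusions on Tierra versus Set.

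Temperature conclusions may well not change. Table B allows a rough within-hiker estimate, because left Tierra and right Set are the same 44 hikers and left Set and right Tierra the same 32. If the entries are means and nobody is missing, Set minus Tierra is [44×(right Set − left Tierra) + 32×(left Set − right Tierra)]/76. This gives +0.13, −0.06 and +0.04 °C dorsal and +0.06, −0.02 and +0.02 °C plantar at the three checkpoints. All are below the thermometer's stated precision of 0.18 °C. The objection is fair, but these figures come from entries rounded to 0.1 °C, and an interval is still missing.

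Two further cautions hold. The first-half figure is provisional, because the Table 3 counts do not reproduce the women's reported blister p-values (chi-square 0.120 against the stated 0.050 on the right foot, 0.056 against 0.042 on the left). The paired estimates are also not adjusted for side, and women were split 25 to 13; with 12 to 16 discordant pairs, an adjusted model would be fragile.

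**Conclusion.** The concern holds. The design supplies 76 randomised Tierra-Set pairs at the start, and no within-hiker contrast is specified or reported. Perimeter results are not shown, so it cannot be said that none was ever run.

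The paired blister data are inconclusive (p=0.146 to 0.210 overall, 0.219 in men) and lean towards more blisters with Set. They neither confirm the men's left-foot result nor show that the models are equal. For temperature, a both-feet paired analysis would roughly halve the variance even at rho = 0, and reduce it further at any positive rho.

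The lesion figures rest on counts rebuilt from rounded percentages and on the 76/31 second-half denominators that those percentages imply; hiker-level data must confirm them. The hiker-level technical versus cotton results are not affected. The change should be made, but the main comparison does not depend on it.

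**What to change.** Add a within-hiker Tierra versus Set analysis using both feet.
- **Lesions:** exact McNemar with the paired odds ratio and its interval, or conditional logistic regression with foot side as covariate where the counts allow.
- **Temperature and perimeter:** Wilcoxon signed-rank on Set minus Tierra per hiker at each checkpoint, with the median difference and its confidence interval.
- **Reporting:** place the paired result beside the men's left-foot finding. Restate that finding as an exploratory three-group subgroup result that the paired comparison does not confirm. Keep technical versus cotton as a between-hiker comparison.
- **Pairs:** state the number analysed at each checkpoint and reconcile which socks the two dropouts wore (74 or 76 second-half pairs).
- **Check while re-running:** the left-foot Tierra-Set p-values at 14.5 km are identical in women and men (0.931 dorsal, 0.287 plantar) although the temperatures differ.

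The cost is a small re-analysis of data already recorded by foot and a check of two records. The p=0.021 claim loses prominence, and the paired lesion result will probably be reported as inconclusive.
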